### **Workstream 2: Data analytic strategy**

The approach we propose for the longitudinal investigation is based on our findings from the IMAGINE-1 study, as well as our longitudinal studies of children with rare CNV. These have indicated that longitudinal follow-up of children with pathogenic CNVs is feasible and informative and that specific childhood factors predict adverse outcomes in adolescence (risk of psychotic disorder). Our analysis indicates that CNV genotype, when included as a factor in our models, explained only 6-22%

of variance in phenotypic outcome, depending on trait. Thus, the majority of the phenotypic variation is not attributable to the CNV but to other factors. It therefore will be important for better understanding of variability in phenotypic outcomes to study the extent to which other genetic variation and environmental risk factors play a role.

Previous work by our group, including a study in collaboration with the 22q11.2DS IBBC, has indicated that Polygenic Risk Scores (PRS) for schizophrenia (derived from a study of patients with that condition) can be used to predict the risk of schizophrenia as an outcome in people possessing pathogenic CNVs. In addition to extrinsic genetic sources of phenotypic variability, the study of characteristics intrinsic to each CNV will also be informative (i.e., CNV size and gene content). For example, previous studies have provided evidence that the number of constrained genes within a CNV may contribute cumulatively to variability in cognitive outcome. Furthermore, there is evidence that the specific gene content of a CNV may also influence risk. Our findings from IMAGINE-1 indicate that children carrying inherited genetic variants are more likely to have neurodevelopmental, emotional and behavioural disorders than children who carry a *de novo* variant. Inherited mutations were associated with higher multiple social deprivation scores, suggesting that the worse outcomes in this group might be reflect the impact of parental mutation (carrier) on the psychosocial environment of these families. Thus, the study of salient environmental factors affecting risk is also likely to be fruitful.

i) We will model the trajectories for the psychopathological and neurocognitive measures using mixed models via an accelerated longitudinal design. We will test several models of longitudinal development including linear and non-linear effects. We have found evidence of considerable psychiatric comorbidity in children with pathogenic CNVs as well as between psychiatric and other neurodevelopmental traits (e.g., motor coordination). We therefore propose to use data reduction strategies as part of our analytical approach, combining highly correlated traits to create phenotypic clusters. We will reduce measures to critical developmental domains by applying principal components analysis to the individual-specific random effects for trajectory generated for each phenotypic measure in the mixed model analysis. This is similar to the approach successfully applied by our team's collaborators to derive measures of disease progression in Huntington Disease and has two main benefits: firstly, defining a more informative phenotypic measure, and secondly, reducing the multiple testing burden.

ii) The domain-specific trajectory measures will be compared between children with pathogenic CNV and their unaffected siblings using regression analysis.

iii) A similar regression analysis will be used to test for differences in trajectories between the 13 different CNVs.

iv) The regression models in ii) will be expanded to include a) polygenic risk scores (PRS), which will be generated using the publicly available summary statistics from large GWAS of schizophrenia, ADHD, ASD and IQ. Each PRS will be regressed against each trajectory measure as described above. These regression models will also consider the effects of environmental factors (e.g., inheritance status of CNV, whether *de novo* or inherited), family socio-economic adversity, family and parent-child relationship quality, parental psychopathology, and experiences of bullying). The effects of environmental factors on the trajectory measures will be tested directly in the regression analyses and we will also be able to include a factor representing change over time in an environmental risk factor. For factors with significant effects (after accounting for multiple testing), their influence in modifying the effects of CNV status on trajectory will be tested by including a CNV\*environmental factor interaction term in the regression. Information on second hits and genetic variation intrinsic to the CNV will be examined in individual models for each CNV only. Where appropriate, we will

investigate whether specific factors influence the analysis above, including family socio-economic status and child history of physical health problems and medication use.

v) Key adolescent outcomes, including prodromal risk for psychosis, internalising disorder and persistence of neurodevelopmental disorders, will be extracted via data linkage, as discussed earlier. The effects of trajectory (and CNV status) on these outcomes will be assessed by logistic regression, considering relevant environmental factors.

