### Workstream 2 inclusion criteria (a subset of IMAGINE-1 Workstream 1):

*Inclusion criteria for 'proband' (e.g. child with rare genetic disorder):*

1. Diagnosis microarray confirmation of a priority CNV
2. Additional consent to take part in the face-to-face interview and home visit
3. Has a legal guardian available who can consent and can provide detailed medical and behavioural history

*Inclusion criteria for control siblings that have taken part in IMAGINE-1 (n=150) are:*

1. Full sibling
2. No pathogenic CNV present
3. Closest eligible sibling in age to the child with CNV

*Inclusion criteria for parents:*

1. Biological parents
2. Additional consent to take part in the face-to-face interview and home visit

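### Workstream 2 analysis iv) builds on the carrier-versus-sibling model, so the CNV status by inheritance interaction cannot be estimated as worded, and CNV genotype is left out

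*Protocol*

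**What the plan says.** All references are to the Protocol.

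- **Item ii)** (section 6.1, Workstream 2: Data analytic strategy): trajectory measures are "compared between children with pathogenic CNV and their unaffected siblings using regression analysis".
- **Item iii)**: "A similar regression analysis will be used to test for differences in trajectories between the 13 different CNVs".
- **Item iv), base model**: "The regression models in ii) will be expanded to include a) polygenic risk scores (PRS". The model named is ii), not iii).
- **Item iv), factors**: "These regression models will also consider the effects of environmental factors (e.g., inheritance status of CNV", specified as de novo or inherited. Socio-economic adversity, relationship quality, parental psychopathology and bullying follow.
- **Item iv), second stage**: "For factors with significant effects (after accounting for multiple testing), their influence in modifying the effects of CNV status on trajectory will be tested" through a product term in the regression.
- **Sibling eligibility** (section 4.4, Workstream 2 inclusion criteria): "No pathogenic CNV present".
- **Genotype** (opening of the Workstream 2 strategy): "CNV genotype, when included as a factor in our models, explained only 6-22" per cent of variance in phenotypic outcome, depending on trait. Genotype enters item iii), and separate per-CNV models are planned for second hits and variation intrinsic to the CNV. It is not a term in ii) or iv).
- **Power**: 500 carriers and 150 siblings for the carrier comparison; 500 participants for polygenic risk scores (PRS), with 3% of variance at alpha 0.0025 and 80% power. This section distinguishes CNV status from CNV genotypes, so the interaction in iv) is with carrier status.

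**The concern.** Item iv) prescribes a test that cannot be run for the factor it lists first. Inheritance is worded as a property of the child's CNV. Siblings have no such CNV, and the plan gives them no coding, so the product of carrier status and inheritance holds nothing that the other columns do not already hold.

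Building on ii) rather than iii) also leaves 13 CNVs pooled in the PRS and inheritance tests. If the inherited share differs between CNVs, the inherited-versus-de-novo contrast partly measures which CNV the child has. The variance that genotype explains stays in the residual of the PRS tests.

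Worse outcomes with inherited variants are a main IMAGINE-1 result in section 4.1 and again in the Workstream 2 strategy, and the follow-up is meant to explain them. The contrast should therefore be specified so that it can be fitted and read without ambiguity.

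**Working it through.** **1. The plan's own figure.** Inputs from Power: n = 500, R² = 0.03, alpha = 0.05/(5 × 4) = 0.0025, one numerator degree of freedom. The noncentrality is n·R²/(1 − R²) = 500 × 0.03/0.97 = 15.46. Against the critical value F(1, 498) = 9.23, the noncentral F gives power of **81.4%** (81.8% by normal approximation). The stated 80% is reproduced.

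With the 650 participants of model ii) the same calculation gives 92.6%, ignoring family clustering. The stated figure therefore fits a carriers-only PRS analysis, although iv) says it expands ii).

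**2. Rank of the interaction model.** The columns are intercept, CNV status C, inheritance I and C × I, for 500 carriers and 150 siblings. The inherited share is taken as 30% of carriers. This is an assumption borrowed from the approximate familial share of the whole IMAGINE-1 cohort in section 4.4; a share of 50% gives the same ranks.

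| Coding of siblings | Rank of 4 columns | Reason |
|---|---|---|
| I = 0 | 3 | C × I = I |
| I = 1 | 3 | C × I = I + C − 1 |
| Missing, dropped | 2 | C = 1 throughout, so C × I = I |
| Family-level value (parent carries the CNV or not) | 4 | I varies in both groups |

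The first three rows treat inheritance as a property of the child's own CNV, as item iv) words it. None allows the interaction to be estimated, and a larger sample would not change that. The fourth row does allow it, but the protocol does not state that coding.

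**3. The main effect.** With intercept, C and I only, and siblings coded 0, the rank is 3 of 3. Without further covariates, the coefficient of I is the inherited-minus-de-novo difference among carriers.

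**4. PRS power with genotype added.** With R²g the share explained by genotype, f² = 0.03/(1 − 0.03 − R²g) and the noncentrality is 500·f². With 13 genotypes the model uses 12 degrees of freedom for genotype and 1 for the PRS.

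- R²g = 0.06: f² = 0.0330, noncentrality 16.5, power **84.6%**.
- R²g = 0.22: f² = 0.0400, noncentrality 20.0, power **92.3%**.

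This assumes that 6-22%, reported for phenotypic outcomes, also holds for trajectory measures.

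**5. Confounding by genotype, illustration only.** The documents give no inheritance rates by CNV. The simulation used 500 carriers, 13 equally frequent CNVs, a mean inherited share of 30%, no true inheritance effect, nominal alpha 0.01 and 4,000 replicates. The share of inheritance variance lying between CNVs is assumed.

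| Assumed share between CNVs | Type I error, genotype 6% | Type I error, genotype 22% |
|---|---|---|
| 5% | 0.014 | 0.029 |
| 10% | 0.016 | 0.052 |
| 30% | 0.042 | 0.159 |

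With genotype as a factor the error is 0.008-0.012 throughout.

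**The case against.** **The question about inheritance is answerable as written.** Item iv) tests each factor directly first; the interaction is a second stage, run only for factors already significant. A reader might infer that the inheritance effect itself cannot be tested. Step 3 shows otherwise, so this objection stands. The defect lies in the follow-up term.

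**Inheritance may be meant as a family characteristic.** Item iv) lists it among environmental factors, and the Workstream 2 strategy suggests that a carrier parent may affect the family's circumstances. Full siblings share that parent. Under family-level coding the interaction is estimable, and siblings would help separate family environment from the child's own CNV. It would therefore be wrong to infer that siblings can never inform this question. What does not stand is treating the coding as settled, because item iv) refers to the CNV's own status and gives no sibling value.

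**Genotype is not ignored, and covariates can be left to an SAP.** Items iii) and the per-CNV models use genotype, and the section on biological sample analysis plans work across four CNV alleles at two loci. An SAP, not available here, could add the factor. But the protocol names ii) as the base model of iv), and neither contains genotype.

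**No harm is demonstrated.** A reader might infer that the PRS analysis is underpowered or that the inheritance result will be biased. The documents support neither: the stated power is met, and the confounding depends on inheritance rates they do not give.

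**Conclusion.** The point holds in two limited parts.

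1. With inheritance defined for the child's own CNV, the prescribed CNV status by inheritance interaction is not estimable in the model that iv) expands: rank 3 of 4, or 2 of 4 if siblings are dropped. This follows from the sibling criterion and needs no numerical assumption beyond both inheritance types occurring among carriers. The interactions for socio-economic adversity, relationship quality, parental psychopathology and bullying are unaffected, because those factors are defined for siblings too.

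2. Leaving genotype out of iv) exposes the inheritance contrast to possible confounding of unknown size and costs the PRS tests some precision. The potential gain from about 81% to 85-92% power is an efficiency gain and rests on carrying 6-22% over to trajectories.

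Both are worth correcting before analysis because the factor needed is already collected. The 500 participants in the PRS power statement also need to be reconciled with the 650 in model ii).

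**What to change.** Reword item iv) of the Workstream 2 strategy in section 6.1:

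- Fit the PRS tests and the inherited-versus-de-novo contrast among carriers, with CNV genotype as a factor. This expands iii) instead of ii) and agrees with the 500 participants in Power.
- Limit the CNV status by factor interactions in the carrier-sibling model to factors defined in both groups.
- If the family-environment effect of a carrier parent is the target, define a family-level variable (parent carries the CNV, yes or no), code it for carriers and siblings alike, and use that in the interaction.

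The cost is wording, with no new assessments. Genotype uses 12 degrees of freedom for the 13 CNVs of item iii), or 15 for the 16 CNVs named under Population, out of about 500 carriers. Siblings leave the own-CNV inheritance contrast, to which they contribute no inheritance information, but would stay in a family-level analysis.

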### 3 Study Synopsis

Title	IMAGINE-2: Stratifying Genomic Causes of Intellectual Disability by Mental Health Outcomes in Childhood and Adolescence
Sponsor name	Great Ormond Street UCL Institute of Child Health
Primary objective	
Baseline assessments were made during IMAGINE-1 (2014-2020).
 
During IMAGINE-2:
 
 
- Workstream 1 aims to map trajectories of developmental risk (at the biological, psychological and social level) over a 5-year period of follow-up from baseline assessments.
 
- Workstream 2 aims to deliver a face-to face follow-up study of young people who have been identified as carrying one of the prioritized high-risk CNVs for mental health and who were seen originally during IMAGINE-1. We aim to identify genetic and environmental contributions to the variability in cognitive and psychopathological variation within participants, both cross-sectionally as well as changes over time.
 

Secondary objective (s)	
Workstream 1:
 
 
- To test hypotheses on potential mechanisms that underlie vulnerability and resilience, exemplified by differentiated trajectories and outcomes.
 
- To provide a framework for the development of personalized preventive interventions that are more effective than current treatments, and which are guided by the individual patient, their psychosocial and educational environment, and their genome.
 
 
Workstream 2:
 
 
- Will study the development of cognition, neurodevelopment and mental health and the impact on these of genetic factors as well as environmental factors such as family function. Workstream 2 will complement Workstream 1 and should enable us identify targets for potential intervention (affecting educational and clinical outcomes).
 

Study Design	
Longitudinal follow-up study of the IMAGINE-1 cohort with two workstreams:
 
 
- Workstream 1 will follow up the whole cohort using online questionnaires on an annual basis and link to administrative records (Hospital Episode Statistics, NHS Digital and National Pupil Database, Department for Education).
 
- Workstream 2 will conduct an intensive face-to-face follow up a subset of the cohort
 

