Baseline	
Conducted as part of IMAGINE-1:
 
Workstream 1:
 
 
- Development and wellbeing questionnaire
 
- Strengths and Difficulties Questionnaire
 
- Adaptive behaviours assessment Schedule -3
 
- Everyday Feelings Questionnaire
 
- Comparison of IMAGINE mental health research data (from Workstream 1 questionnaires) with the Mental Health Children and Young People data of the general population (MHCYP, anonymous data from NHS Digital)
 
 
Workstream 2:
 
 
- Modified Lewis scale
 
- Child and Adolescent Psychiatric Assessment (CAPA)
 
- Autism Diagnostic Interview–Revised (ADI-R)
 
- Structured interview for Prodromal Symptoms (SIPS)
 
- Autism Diagnostic Observation Schedule (ADOS)
 
- Wechsler Abbreviated Scales of Intelligence-2nd Edition (WASI-II)
 
- Developmental Behaviour Checklist (DBC)
 
- Wisconsin Card Sorting Test (WCST)
 
- Cambridge Neuropsychological Test Automated Batter (CANTAB)
 
- Family Environment Scale
 
- Iowa Family Interaction Rating Scales
 
- Life Events Checklist
 
- Physical Health (including seizures and epilepsy) and medication use
 
- Development Coordination Disorder Questionnaire (DCDQ)
 
- Strengths and Difficulties Questionnaire (SDQ – parent and teacher reports)
 
- Social Communication Questionnaire (SCQ)
 
- Social Responsiveness Scale (SRS)
 
- Repetitive Behavior Scale Revised (RBSR)
 
- Pubertal development (Peterson assessment)
 
- Child Eating Behaviour Questionnaire (CEBQ) and the Hyperphagia Questionnaire (HQ)
 
- Epilepsy screening questionnaire (ESQ)
 
- Blood and saliva sample collection
 

Longitudinal follow up	
Workstream 1:
 
 
- Data linkage to Hospital Episode Statistics (HES)
 
- and Comparison of HES data of the IMAGINE and
 

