	
control cohorts (pseudonymised control data from individuals without intellectual disability, NHS Digital)
 
- Data linkage to National Pupil Database (NPD)
 
- Development and Wellbeing questionnaire
 
- Annual follow-up (for 5 years):
 
 
- Strengths and Difficulties Questionnaire
 
- Everyday Feelings Questionnaire
 
- Adaptive behaviours assessment Schedule
 
- Family Life Questionnaire
 
- Wessex Scales
 
- Demographic updates
 
- Impact of COVID-19 on mental health
 
- Study Impact Questionnaire
 
 
Workstream 2:
 
 
- Modified Lewis scale
 
- Child and Adolescent Psychiatric Assessment (CAPA)
 
- Autism Diagnostic Interview–Revised (ADI-R)
 
- Structured interview for Prodromal Symptoms (SIPS)
 
- Autism Diagnostic Observation Schedule (ADOS)
 
- Wechsler Abbreviated Scales of Intelligence-2nd Edition (WASI-II)
 
- Developmental Behaviour Checklist (DBC)
 
- Wisconsin Card Sorting Test (WCST)
 
- Computerised Neurocognitive Battery (CNB)
 
- Family Environment Scale
 
- Iowa Family Interaction Rating Scales
 
- Life events checklist
 
- Physical Health (including seizures and epilepsy) and medication use
 
- Development Coordination Disorder Questionnaire (DCDQ)
 
- Strengths and Difficulties Questionnaire (SDQ – parent and teacher reports)
 
- Social Communication Questionnaire (SCQ)
 
- Social Responsiveness Scale (SRS)
 
- Repetitive Behavior Scale Revised (RBSR)
 
- Pubertal development (Peterson assessment)
 
- Child Eating Behaviour Questionnaire (CEBQ)
 
- Hyperphagia Questionnaire (HQ)
 
- Epilepsy screening questionnaire (ESQ)
 
- Blood and saliva sample collection
 
- Eating Disorder Examination Adolescent Questionnaire (EDE-A)
 
- Pica, ARFID, and Rumination Disorder Interview (PARDI-AR-Q)
 
- ARFID brief screener (ARFID-BS)
 
- Nine Item ARFID screen (NIAS)
 

--	--

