## 4.3 Study Design

We are conducting a 5-year longitudinal study of the cohort with annual online phenotyping of all participants and linking to administrative records (Workstream 1), supplemented by intensive face-to-face assessments of 520 young people with highly pathogenic CNV that were intensively studied in our first phase (Workstream 2). Two research centres are involved: University College London's Great Ormond Street Institute of Child Health and Cardiff University's Neuroscience and Mental Health Research Unit.

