#### Interview-assessed child psychopathology:

- The Child and Adolescent Psychiatric Assessment (P-CAPA; Angold et al, 1995): will be conducted with the main-caregiver. The CAPA (duration 2-3 hours) provides DSM-IV and ICD-10 diagnoses of all behavioural and psychiatric problems (including detailed assessment of psychotic symptoms), except autism. A child self-report version of the CAPA (C-CAPA) will be used with the children to ascertain psychotic symptoms, mood and anxiety symptoms
- Structured interview for Prodromal Symptoms (SIPS; Miller et al., 2002): conducted with older children to obtain information on prodromal psychosis symptoms.
- Autism Diagnostic Interview–Revised (ADI-R; Rutter et al., 2003): will be conducted where screening by SCQ is positive (duration 1-2 hours). If probands screen positive for autism, in combination with the ADI-R interview conducted with the parents, we will offer the parent the possibility to conduct an observational assessment of the child, to establish autism, using the Autism Diagnostic Observation Schedule (ADOS; Lord et al., 1989). The ADOS is a semi-structured, standardised assessment of communication, social interaction and play. It provides a series of standardised contexts in which the child's social, communication and repetitive, stereotyped behaviours can be observed. Standardised toys and activities are used to present opportunities for social and communicative interaction with the examiner.
- Where appropriate, an interview section [completed via parent and/or child self-report depending on clinical context and child's verbal ability] about eating disorders will be conducted using the Eating Disorder Examination Child version (Bryant-Waugh et al 1996) and the PARDI (Bryant-Waugh et al 2019, The Pica, ARFID (Avoidant Restrictive Food Intake Disorder), and Rumination Disorder Interview).

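### Workstream 2 item v) draws its three key adolescent outcomes from data linkage, yet no linked source for them is described, while the protocol's own follow-up interviews assess them

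*Protocol*

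**What the plan says.** Section 6.1, Workstream 2, item v) names the source of the outcomes: "Key adolescent outcomes, including prodromal risk for psychosis, internalising disorder and persistence of neurodevelopmental disorders, will be extracted via data linkage, as discussed earlier". It then gives the model: "The effects of trajectory (and CNV status) on these outcomes will be assessed by logistic regression, considering relevant environmental factors".

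The linkage is set out under Workstream 1. In the Synopsis (section 3), that workstream "will follow up the whole cohort using online questionnaires on an annual basis and link to administrative records", namely HES and the NPD. Section 4.3 makes the same assignment.

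Workstream 2 has its own instruments. Section 5.5 includes the SIPS, "conducted with older children to obtain information on prodromal psychosis symptoms". It also includes the CAPA for psychiatric diagnoses other than autism, with a child version for psychotic, mood and anxiety symptoms. The SCQ screens for autism; the ADI-R follows a positive screen, and the ADOS is then offered. Section 5.4 lists the same interviews at baseline.

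**The concern.** The reference back to earlier text leads only to a Workstream 1 linkage that is not described as producing these outcomes. If v) is followed as written, an interview-rated state has no described source. The other two outcomes would be known only for young people whose condition reached a service and was recorded there. Associations with trajectory and CNV status could then partly reflect who was recognised and treated, not who developed the condition. Section 4.1 itself poses as an open study question how far local services recognised and treated these children's conditions, so complete recognition cannot be assumed when defining the outcome. Meanwhile the follow-up visit collects direct assessments that v) does not name.

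**Working it through.** The plan gives no event count, capture rate or power for v), so there is no stated figure to reproduce. The check is a comparison of the protocol's own text.

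1. **What the linkage is for.** The Synopsis lists "Data linkage to Hospital Episode Statistics" and a matching NPD entry under Workstream 1 follow-up. In the Workstream 1 part of section 6.1, HES supplies patterns of healthcare use, incidence of hospital episodes, and clusters and trajectories of use. Mental health problems appear there only as a characteristic to be accounted for. The NPD is given no outcome in section 6.1. Nothing before v) defines any of its three outcomes from a linked record.

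2. **What the visit supplies.**
   - *Prodromal risk:* SIPS, older children only.
   - *Internalising disorder:* CAPA.
   - *Persistence of neurodevelopmental disorder:* CAPA for disorders other than autism. For autism, SCQ, then ADI-R and ADOS where the screen is positive. The ADI-R alone would not be enough, because it covers autism only.
   - Persistence needs status at both visits. The plan has baseline and one follow-up about five years later (section 5.5).

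3. **How Workstream 1 does it.** The workstream that owns the linkage bases onset of new psychiatric disorder on the DAWBA and on SDQ/ABAS-3, not on records (section 6.1, second step).

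4. **Who lacks a linked outcome.** Section 5.2 (Specific consent) lets families accept face-to-face visits and decline linkage. They could have full interview data and no outcome for v). No linkage is described for the control siblings either, which matters if CNV status in v) means carrier versus sibling, as in ii).

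5. **Overlap if the source is changed.** Item i) builds trajectories from the psychopathological and neurocognitive measures, then combines them by principal components. With one follow-up visit, a CAPA outcome at that visit would also sit inside a CAPA-based trajectory. The exclusion therefore has to be made before the principal components step.

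6. **Illustration only.** The group sizes (500 and 150) and alpha of 0.01 come from the Power section. Every other value is an assumption.
   - With a true frequency of 20%, 500 × 0.20 = 100 cases. Capture of 10% to 30% records 10 to 30 of them.
   - With equal true risk of 20% and capture of 20% versus 10%, recorded risks are 4% and 2%. The odds ratio is (0.04/0.96)/(0.02/0.98) = 2.04 with no true effect. This largely restates the assumed twofold capture.
   - For true risks of 20% versus 5% and no false positives, power = Φ[(|p1 − p2| − 2.576·SE0)/SE1], with SE0 pooled and SE1 unpooled. At 50% capture, p1 = 0.10 and p2 = 0.025, so SE0 = 0.0256, SE1 = 0.0185 and power = 0.69. At 100, 75, 50, 25 and 10% capture, power is 0.99, 0.93, 0.69, 0.22 and 0.03.

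**The case against.** The strongest reply has four parts.

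- **A reader might infer that linkage cannot supply any of the three outcomes.** The documents do not show this. They do not describe the diagnostic content of HES or the NPD, and records may hold internalising or neurodevelopmental diagnoses for those who reached services. Only for prodromal risk does the protocol's own choice of an interview measure make the gap plain. This part of the reply stands.
- **A reader might also infer that the interviews are discarded, or that an unrecorded condition is coded as absent.** Neither is stated. Item v) names no other source, but i) uses the psychopathological measures, and coding rules may sit in an analysis plan that is not shown. This stands too.
- **Linkage has real advantages.** Under the no-further-contact option in section 5.7, linked data can still be obtained after visits stop. A separate source also keeps outcome and predictor apart. Both are reasons to keep linkage, but not as the sole named source of outcomes it is not described as providing.
- **Interview coverage is not universal.** The SIPS is age-limited and the ADI-R is screen-dependent. The COVID-19 adjustments allow a reduced set of measures, naming only the CAPA and questionnaire pack as adaptable online. That is a genuine limit of the fix.

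Item v) also adjusts for environmental factors, which may reduce ascertainment differences related to deprivation. It cannot restore cases that were never recorded.

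**Conclusion.** The point holds as an internal mismatch with a practical consequence. Item v) names a source for which the protocol describes none of the three outcomes, and leaves unnamed the assessments that address them. For prodromal risk no linked source is described. For the other two outcomes, capture would be incomplete and dependent on service contact, and absent where linkage is declined.

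The size of any bias or loss of power cannot be derived from the documents. The illustrative figures rest on assumed frequencies and capture rates and show only that the result depends heavily on capture. Nor does the point undermine Workstream 2 as a whole: items i) to iv) do not rely on linkage for their outcomes, and the stated power calculations concern trajectories, not the binary outcomes in v). It should be corrected before v) is analysed.

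**What to change.** Rewrite v) as follows.

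- **Primary outcomes from the follow-up research assessments.** SIPS for prodromal risk, in those old enough to receive it. CAPA for internalising disorder. For persistence, status at both visits: CAPA for non-autism neurodevelopmental disorders, and SCQ with ADI-R/ADOS where screen-positive for autism.
- **Linked HES and NPD records as a supplementary or sensitivity source**, including for participants not reassessed, with a stated definition for each outcome taken from them.
- **Trajectory kept as the predictor**, but with the outcome's own instrument or domain (or its follow-up score) removed from the trajectory used to predict it. Replacing trajectory with baseline measures is unnecessary and would change the question v) asks.

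The cost is a revised item v) and some re-derivation of trajectories, since the exclusion differs by outcome. No new data collection is needed. The downside is that the primary outcomes cover only participants reassessed with the relevant instrument, so the number assessed should be reported for each outcome.
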